3.0 Objectives

- 3.1 **For phase I portion of study:** To determine the tolerability of the combination of idarubicin, cytarabine (ara-C), and nivolumab (IAN) in patients with high-risk MDS and AML.
- 3.2 **For phase II portion of study:** To determine event-free survival (EFS) where the events is defined as death or relapse using the combination of idarubicin, cytarabine, and nivolumab in patients with high-risk Myelodysplastic syndrome (MDS) and Acute Myeloid Leukemia (AML).

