5.0 Treatment Plan

5.1 **General:** All patients should be registered with PDMS. Information pertaining to important prognostic factors such as age, performance status and prior therapy will be recorded.

5.2 **Treatment Schedule:** (Each cycle is approximately 28-35 days)

a. **Phase I**

Nivolumab dosed as indicated below starting approximately on day 24 ± 2 days

Idarubicin 12 mg/m² IV over 15 to 30 minutes daily x 3 (days 1-3)

ara-C 1.5 g/m² IV over 24 hours daily (days 1-4)

Solumedrol 50 mg or dexamethasone 10 mg IV daily for 3-4 days with ara-C (days 1-4)

All patients may receive a second induction course at the discretion of treating physician.

The dose of investigational agent, that is, Nivolumab, will be escalated in successive cohorts of patients. Patients will be entered sequentially to each dose level. If none of the first 3 patients at a dose level experience first cycle dose-limiting toxicity (DLT), new patients may be entered at the next higher dose level. If 1 of 3 patients experience first cycle DLT, up to 3 more patients are started at that same dose level. If 1 of 6 experience DLT, then new patients may be entered at the next higher dose level. If 2 or more experience first cycle DLT, no further patients are started at that dose. The MTD is the highest dose level in which <2 patients of 6 develop first cycle DLT. The following table lists out the 3 dosage levels that will be used in the study, and the starting dose is 1mg/kg IV of Nivolumab. There will be no intra-patient dose escalation for Nivolumab.

The enrollment of participants will be staggered; all the participants in each cohort will be observed for approximately 3 weeks from the first dose of Nivolumab before proceeding to the next cohort.

Dose of nivolumab will be as follows:

Dose level	Nivolumab (mg/kg IV)	No of patients
-1	0.3	3
0	1	3
1	3	3

b. **Phase II** (Each cycle is approximately 28-35 days)

Patients will receive 1 or 2 induction cycles of therapy according to the following starting schedule:

Nivolumab starting approximately on day 24 \pm 2 days at a dose defined by Phase I portion of the study but it is expected that the dose 3 mg/kg will be selected based on prior studies.

Idarubicin 12 mg/m² IV over 15 to 30 minutes daily x 3 (days 1-3)

ara-C 1.5 g/m² IV over 24 hours daily (days 1-4) (days 1-3 for patients older than 60)

Solumedrol 50 mg or dexamethasone 10 mg IV daily for 3-4 days with ara-C (days 1-4) (days 1-3 for patients older than 60).

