8.0 Evaluation During Study

- 8.1 CBC, platelet, differential (if WBC $> 10^9/L$) every 4-7 days during remission induction and every 1 to 4 weeks during maintenance therapy.
- 8.2 Bone marrow aspirate and cytogenetics and molecular studies (if abnormal at start) on day 21-28; then aspirate every 1-2 weeks as required until CR; then every 3-6 months in year 1 if deemed necessary by the treating physician. Bone marrow aspiration may be omitted in patients where there is clear evidence of active disease (e.g., persistent blasts in peripheral blood).
- 8.3 Creatinine, total bilirubin and SGPT, PT, PTT, and INR every 1-2 weeks during induction then every 4-8 weeks on study.
- 8.4 Blood samples (10cc)/bone marrow (optional studies, see Section 14)
- 8.5 End of Study: History and physical exam
End of study evaluation will be performed after the completion of the maintenance therapy, or any time before that if the patient withdraws from the study or the treatment is discontinued for toxicity or disease relapse/progression.

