12.3 Phase 2 study

The primary outcome of this trial is event-free survival (EFS) which is defined as the time from the treatment start till treatment failure, relapse, or death whichever comes first.. The treatment failure is defined as not achieving CR after two cycles of treatment. If the patient achieves remission after the treatment, the relapse occurred in the later time would be considered as "event". We will monitor the EFS as patients accrue and are evaluated. The chemo-naïve patients under MTD in phase I will be included in the phase 2 study.

The monitoring uses the Bayesian method of Thall, et al [2005]. It will be assumed that EFS follows an exponential distribution with median m_T under the current treatment. The

historical median of EFS is denoted by m_H given an historical (H) treatment. For priors, we assume the conjugate inverse gamma (IG) priors $m_T \sim \text{IG}(a_T, b_T) = \text{IG}(3.2, 15.6)$ and $m_H \sim \text{IG}(a_H, b_H) = \text{IG}(124.5, 864.5)$. Both priors have mean of 7 months while $\text{var}(m_T) =$

40 and $\text{var}(m_H) = 0.40$. That is, the prior on m_T is non-informative while the prior on m_H is informative. The trial will be monitored and will be stopped early if, based on the data available at the time, it is unlikely that the median EFS rate will be at least 7 months. The monitoring is continuous monitoring starting from the 1st patient.

$\Pr(\text{median EFS under treatment} \geq \text{median EFS under historical treatment} \mid \text{data from the trial}) < 0.03$.

The operating characteristics of this rule for $N_{\text{max}} = 75$ patients, computed assuming a 5 patient/month accrual rate and 24 months of follow up after the last patient is accrued, *The operating characteristics* are given in the following table.

Table 13.2 Operating characteristics. *The operating characteristics for the EFS monitoring rule are summarized in the following table.*

Simulation Results		
Median months to death or relapse	Pr(Stop early)	Mean # pats. (25%, 75% percentiles)
5	0.8	51.3 (31,75)
7	0.11	70.5 (75,75)
9	0.02	73.9 (75,75)

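### Table 13.2 contains no induction failures, although section 12.3 counts them as EFS events, so the stopping rule's stated properties are not shown for the endpoint it monitors

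*Combined protocol and SAP*

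**What the plan says.** - **Event definition, section 12.3.** EFS runs from treatment start to treatment failure, relapse or death. On failure: "The treatment failure is defined as not achieving CR after two cycles of treatment".
- **Event definition, section 3.2.** The phase II objective leaves failure out: "To determine event-free survival (EFS) where the events is defined as death or relapse".
- **Model and rule, section 12.3.** "It will be assumed that EFS follows an exponential distribution with median" m_T, with prior IG(3.2, 15.6). The comparator is described thus: "historical median of EFS is denoted by m_H given an historical (H) treatment", with prior IG(124.5, 864.5), mean 7 months. The trial stops if the posterior probability that m_T is at least m_H falls below 0.03. Monitoring is continuous, with at most 75 patients, 5 per month and 24 months of follow-up after the last.
- **Table 13.2.** The rows are labelled "Median months to death or relapse". At 5, 7 and 9 months it gives Pr(stop) 0.80, 0.11 and 0.02 and mean N 51.3, 70.5 and 73.9.
- **Timing.** Section 5.2: "Each cycle is approximately 28-35 days" and "Patients will receive 1 or 2 induction cycles of therapy according to the following starting schedule". Section 8.2 schedules marrow aspirates "on day 21-28; then aspirate every 1-2 weeks as required until CR".
- **CRp.** Section 5.8 takes patients off study after two courses only if they have neither CR nor CRp. Section 12.3 names CR alone.

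The plan gives no assumed non-CR share, no explicit rule for dating a failure, and no source or event definition for the 7-month historical median.

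**The concern.** Section 12.3 creates a group of events at a fixed assessment, about two cycles after treatment start. A constant hazard has no such group. If the table was simulated from a constant hazard alone, its stopping probabilities and sample sizes describe a different event-time distribution from the one the rule will meet.

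This is the plan's only formal stop for lack of efficacy; the other rule in section 12.3 concerns toxicity. Those who approve and run the trial rely on its stated ability to separate a 5-month from a 7-month regimen (0.80 against 0.11, a gap of 0.69). If that does not hold, they may continue with a poor regimen or stop an acceptable one without knowing how likely either error is.

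**Working it through.** **1. The rule.** An exponential with median m has rate ln2/m. With d events and total exposure T, the posterior is m_T ~ IG(3.2 + d, b), where b = 15.6 + ln2 × T. Hence Pr(m_T ≥ m_H) = BetaCDF(b/(b + 864.5); 3.2 + d, 124.5), and the trial stops if this is below 0.03. The prior means are 15.6/2.2 = 7.09 and 864.5/123.5 = 7.00, as stated after rounding.

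**2. Reproducing Table 13.2.** Simulated with 75 patients, one every 0.2 months, a look at each arrival and one look 24 months after the last. A single exponential gives Pr(stop) 0.81/0.12/0.02 and mean N 49.7/70.1/73.9. With random arrivals it gives 0.798/0.109/0.020 and 50.8/70.5/73.9. The table is therefore right for its own model, and that model has no failure component.

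**3. Inputs for the illustration.**
- Failure date: two cycles of 28-35 days are 56-70 days, or 1.84-2.30 months (section 5.2).
- Non-CR share: assumed 30-40%, the complement of the 60-70% background CR rate in section 2.1b. A 20% share is also tried, the complement of the upper end of the 70-80% given there for younger diploid patients.

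**4. Why the result can move either way.** Take 30% failing at 1.84 months, independently of the other events, with a constant hazard λ from treatment start. The EFS median is m when 0.7 × exp(−λm) = 0.5, so λ = ln(1.4)/m.
- m = 7: λ = 0.0481. By 1.84 months a share 1 − 0.7 × 0.915 = 0.359 has had an event, over 1.76 months of exposure per patient. The exponential fit at that point is 0.693 × 1.76/0.359 = 3.4 months, which pushes early looks towards a false stop.
- m = 5: λ = 0.0673. The mean event time is 0.7/0.0673 + 0.3 × 0.116/0.0673 = 10.9 months. With full follow-up the fit tends to 0.693 × 10.9 = 7.6 months, so a 5-month regimen comes to look acceptable.

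**5. Results, Pr(stop).** In rows (a) to (c) the months are the median of EFS as section 12.3 defines it.

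| Scenario | 5 | 7 | 9 |
|---|---|---|---|
| Table 13.2 | 0.80 | 0.11 | 0.02 |
| Single exponential | 0.81 | 0.12 | 0.02 |
| (a) 30-40% failing at 1.84-2.30 months, independent of other events | 0.22-0.51 | 0.03-0.31 | 0.01-0.24 |
| Example of (a): the case in step 4 | 0.51 | 0.25 | 0.16 |
| (b) 30% failing at 1.84-2.30 months, being those who would have had the earliest events | 0.80 | 0.15-0.18 | 0.05-0.09 |
| (c) 20% failing at 2.07 months, no events before then | 0.80 | 0.03 | 0.005 |

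Row (a) covers two versions of the other patients' hazard: starting at treatment start, or only at the failure date. Random arrivals raise its upper ends at 7 and 9 months to roughly 0.35 and 0.30. In row (b) the gap between 5 and 7 months is about 0.62-0.66. For row (c) at dates from 1.84 to 2.30 months the gap is about 0.70-0.85, equal to or better than the stated 0.69.

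**6. The header taken literally.** If 5/7/9 are medians to death or relapse and failures are added on top, Pr(stop) at 7 months with 30-40% failing depends on how failure and death are related:
- about 0.14-0.38 if the failures are those who would have died or relapsed earliest;
- 0.42-0.84 if non-CR patients have an assumed median survival of 2 or 4 months;
- about 0.85-0.99 under independence.

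All of these exceed the stated 0.11.

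**The case against.** The strongest reply is that the header is loose wording. Section 12.3 puts the exponential on EFS just after defining it, the table caption refers to the EFS monitoring rule, and the rule compares two median EFS values. Giving operating characteristics under a declared working model is normal practice, and section 12.1 presents the trial as a very early look at efficacy. The CR rates used here are general background, not rates for this regimen or for the age range in section 4.2.

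Much of this stands. Reading the rows as median EFS is reasonable, and rows (a) to (c) adopt it. The 30-40% share is an assumption. What does not stand is that the working model settles the matter: it may drive the rule, but section 12.3 itself places events at a fixed assessment, and the figures can change materially once they are included.

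Four stronger readings are tempting, and the documents do not support them:
- *The table is miscalculated.* It is reproduced.
- *With 30-40% failures the rule must lose most of its discrimination.* Row (b) keeps nearly all of it at 30%.
- *Under the literal header the rule would almost always stop a 7-month regimen.* That needs failure to be independent of death, yet patients without CR include early deaths that a death-or-relapse median already counts.
- *Failures could all be dated at the end of cycle 1, giving many more false stops.* Section 5.2 allows one induction cycle, but sections 5.8, 11.1 and 12.3 all refer to two.

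**Conclusion.** The point holds as a mismatch that should be fixed. Sections 3.2 and 12.3 and the Table 13.2 header do not share one event definition, and the table's Pr(stop) and mean N are not shown to hold for the endpoint that is monitored. Confidence in this is high.

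The size is assumption-dependent. It ranges from a large loss of separation (row (a)), through little change apart from more false stops (row (b)), to separation as good as or better than stated (row (c)). Four things decide it: the non-CR share, the date given to failure, the dependence between failure and death, and the event definition behind the 7-month median. The plan puts the failure date at roughly 56-70 days at the earliest but gives no exact rule; the other three are not stated. No single direction of error can be claimed.

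A reader might also infer that the primary efficacy estimate is biased. It is not affected: section 12.4 estimates EFS by Kaplan-Meier, which assumes no constant hazard. The consequence is confined to the stop-or-continue decision.

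**What to change.** 1. Use one EFS event definition in section 3.2, section 12.3 and the Table 13.2 header, and say whether CRp counts as failure for EFS.
2. State the date assigned to treatment failure, including for patients who receive only one induction cycle.
3. State the assumed non-CR share, and the source and event definition of the 7-month historical median.
4. Re-simulate Table 13.2 with the failure component, including a stated assumption on how failure and death are related. Restate Pr(stop) and mean N at 5, 7 and 9 months.
5. Revisit the 0.03 cutoff only if the restated figures are unacceptable.

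The cost is statistician time and a few wording changes. No extra patients or data are needed, and the monitoring tool changes only if the cutoff does. The restated figures may be less favourable than the present ones.

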The Department of Biostatistics at MD Anderson will provide and maintain a website (“Clinical Trial Conduct”: <https://biostatistics.mdanderson.org/ClinicalTrialConduct/>) for patients enrolled on this study. The Clinical Trial Conduct website resides on a secure server, and access is gained through usernames and passwords provided to personnel responsible for enrolling patients and updating patient data. The website is accessed through a browser using secure socket layer (SSL) technology. Personnel responsible for enrolling patients on trials, which includes the principal investigator(s), research nurse(s), and data coordinator(s), will be trained by members of the Department of Biostatistics in the use of the trial website; the importance of timely updating of follow-up times and recording of events will be emphasized in training.

We will also monitor the unacceptable nivolumab grade 3 or 4 drug attributable toxicity rate by 12 months, and we will stop the trial if we have statistical evidence that this unacceptable toxicity rate is more than 10%. The method of Thall, Simon and Estey [1995] will be used for toxicity monitoring for this study. The software Multc Lean.Version 2.1 was used to run the simulation.

We will stop the trial early if

$P(\text{unacceptable toxicity by 12 months} > 10\% \mid \text{data from the trial}) > 0.95$.

That is, given the outcomes from the patients who have already been evaluated, if we determine that there is more than a 95% chance that the unacceptable toxicity rate is more than 10%, we will stop the trial. This decision rule gives the following stopping rule. We assume a beta(0.2, 1.8) prior distribution for the unacceptable toxicity rate.

The operating characteristics of this decision rule are shown in Table 2. When the trial is completed we will report the posterior probability that the unacceptable toxicity rate by 12 months is more than 10%, and we will give a 90% credible interval for this rate.

Table 13.3. toxicity stopping boundaries in cohort size of 5.

Number of patients	Stop the trial if there are this many patients achieving toxicity
5	3-5
10	4-10
15-20	5-20
25	6-25
30	7-30
35-40	8-40
45	9-45
50-55	10-55
60	11-60
65-70	12-70

Table 13.4: Operating characteristics for monitoring of toxicity rate.

True toxicity Rate	Early Stopping Probability	Average number of patients treated
0.05	0.01	75
0.1	0.11	70
0.15	0.47	56
0.2	0.83	38

0.25	0.97	25
------	------	----

12.4 Analysis plan:

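### Table 13.4's average numbers treated (38 at 20% toxicity, 25 at 25%) assume each 12-month outcome is known at once; at 5 patients a month with early exits they are about 63 and 56

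*Combined protocol and SAP*

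**What the plan says.** Section 12.3 defines the monitored toxicity over a 12-month window: "We will also monitor the unacceptable nivolumab grade 3 or 4 drug attributable toxicity rate by 12 months". The trial stops if the posterior probability that the rate exceeds 10% is above 0.95, under a beta(0.2, 1.8) prior. The rule is applied "given the outcomes from the patients who have already been evaluated"; the section does not say when a patient counts as evaluated.

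Table 13.3 gives "toxicity stopping boundaries in cohort size of 5", from 3 of 5 up to 12 of 70. Table 13.4 gives, for true rates of 5/10/15/20/25%, early stopping of 0.01/0.11/0.47/0.83/0.97. Its column headed "Average number of patients treated" reads 75/70/56/38/25.

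No accrual rate is stated for Table 13.4. The EFS simulation for the same maximum of 75 patients was "computed assuming a 5 patient/month accrual rate and 24 months of follow up after the last patient is accrued". In phase I, section 5.2 staggers enrolment: "all the participants in each cohort will be observed for approximately 3 weeks from the first dose of Nivolumab". No enrolment pause is stated for phase II.

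**The concern.** A toxicity-free patient cannot be classified on a by-12-months endpoint on the day of entry. If accrual continues while outcomes are pending, many more patients will have been enrolled when a boundary is crossed than the number on whom the decision rests. The average number treated tells an oversight body how many patients would be exposed to an unacceptably toxic regimen before the rule acts. If that column ignores the outcome delay, it overstates the protection given by phase II's only statistical toxicity stopping rule.

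**Working it through.** **Inputs.** Prior, cutoff, 12-month window and looks every 5 patients: section 12.3. Maximum 75: the EFS design, consistent with the mean of 75 in Table 13.4. Accrual of 5/month and an exponential EFS with 7-month median: EFS part of section 12.3. Departure for no CR/CRp after two courses or for progression: sections 5.8 and 11.1. Onset times: assumptions, because the documents give none.

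**1. Reproduce the plan.** The boundary at n is the smallest x with P(rate > 0.10 | beta(0.2 + x, 1.8 + n − x)) > 0.95. This gives 3, 4, 5, 5, 6, 7, 8, 8, 9, 10, 10, 11, 12, 12 at n = 5, 10, …, 70, matching all 14 in Table 13.3. Exact binomial recursion, with every outcome known at each look, gives:
- stopping 0.005/0.109/0.471/0.829/0.970;
- mean number 74.7/70.3/55.9/38.1/25.4.

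This is Table 13.4, within rounding or simulation error (0.005 against the printed 0.01). Looks after every patient would give 31.3 and 19.6 at 20% and 25%, so the table is the cohort-of-5 rule with no outcome delay.

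**2. Extreme case: everyone evaluated only at month 12, 5/month.** Look n falls at (n − 1)/5 + 12 months: 12.8, 13.8 and 14.8 months for n = 5, 10 and 15. By then 65, 70 and 75 patients are enrolled (one fewer each if the patient due at that instant is not counted). Only the first two looks, or three on the second convention, can save enrolment.
- At 20%, stopping at the first two looks has probability 0.058 and 0.080. Mean = 75 − 10(0.058) − 5(0.080) = 74.0.
- At 25%, these are 0.104 and 0.141. Mean = 75 − 10(0.104) − 5(0.141) = 73.3.

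On the second convention the means are 73.8 and 72.9. Stopping during accrual is 0.14–0.21 at 20% and 0.25–0.36 at 25%.

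**3. With early exits, 5/month.** Each patient is evaluated at the earlier of month 12 and EFS event plus 1 month. EFS is taken as independent of toxicity, and no toxicity is counted before evaluation. With a 7-month median, 1 − 2^(−11/7) = 0.66 of patients are evaluated before month 12, and the first look comes at about 28 enrolled. By simulation, mean enrolment is about 63 at 20% and 56 at 25%, and stopping during accrual is about 0.54 and 0.77. Overall stopping stays about 0.83 and 0.97 if looks continue through follow-up.

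**4. Slower accrual, with exits.** About 50 and 39 at 2/month; about 45 and 32 at 1/month (simulation, within about 1 patient).

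**5. Toxicities counted at onset, toxicity-free patients at exit or month 12, 5/month.** A toxicity is taken to appear at its assumed onset whether or not the patient has left.

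| Counting rule | Mean at 20% | Mean at 25% | Stop at true 10% |
|---|---|---|---|
| Table 13.4 as printed | 38 | 25 | 0.11 |
| Exit or month 12 (step 3) | 63 | 56 | 0.11 |
| Month 12 only (step 2) | 74 | 73 | 0.11 |
| At onset, spread over 12 months, exits | 57 | 50 | about 0.19 |
| At onset, within 3 months, exits | 31 | 25 | about 0.56 |

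With onset over 12 months and no exits, stopping at a true 10% rate is about 0.67. Toxic patients enter the denominator sooner than toxicity-free ones, which inflates the observed rate. None of these rules recovers the whole printed table at 5/month.

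**The case against.** Four points on the other side deserve weight.

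- **Early departures.** A reader might infer from step 2 that accrual is all but complete before the rule can act, and quote 74 and 73 as the result. The documents do not support that as the main figure: patients leave for non-response or progression, and under the plan's own 7-month median 1 − 2^(−12/7) = 0.70 have an EFS event before month 12. Evaluating them at exit brings the means down to about 63 and 56. A gap to 38 and 25 remains.
- **Toxicities already seen.** Once a toxicity occurs, that patient's outcome is settled, and the plan says of its trial database that "the importance of timely updating of follow-up times and recording of events will be emphasized in training". Counting at onset can bring the means close to those printed, but stopping at a 10% rate then no longer matches 0.11.
- **Borrowed accrual rate.** The 5/month figure is an input to the EFS simulation, not an enrolment forecast. Slower accrual narrows the gap without closing it at the rates tested.
- **Carry-over.** The plan states: "The chemo-naïve patients under MTD in phase I will be included in the phase 2 study". In the extreme case, six such patients with a head start of 1 to 12 months leave the mean at 25% between about 73 and 67.

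A reader might also infer that Table 13.4 is miscalculated or that the rule cannot stop a toxic trial. Neither follows. The arithmetic is right for immediate outcomes, and overall stopping is unchanged in steps 2 and 3. A stop after accrual still helps patients on nivolumab, which runs for up to 1 year.

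**Conclusion.** The concern holds for the average-number-treated column. At 5/month, 38 and 25 become about 63 and 56 with early exits, and about 74 and 73 as an upper extreme. The chance of stopping while enrolment can still be saved is about 0.54 and 0.77, or 0.14–0.21 and 0.25–0.36 in the extreme case. Counting toxicities at onset trades this for a higher false-stop rate.

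The sizes rest on the borrowed accrual rate, uninterrupted accrual, a 7-month exponential EFS independent of toxicity, evaluation one month after an EFS event, and assumed onset times. That the printed table contains no outcome delay depends on none of these.

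This should be fixed, but it is not evidence of absent oversight: individual discontinuation criteria (section 5.10.3), SAE reporting (section 10) and EFS monitoring (section 12.3) all operate. The harm is a safeguard described as more protective than it is.

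**What to change.** In section 12.3:

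1. State when a patient counts as evaluated. Cover whether a toxicity counts at onset, how a toxicity-free patient with under 12 months counts, and how patients who leave early count.
2. Re-run Table 13.4 under that rule with the 12-month window, a stated accrual rate (5/month and slower), early exits and a range of onset times.
3. Replace the average-number-treated column, and the stopping probabilities where the chosen rule changes them. Report stopping during accrual separately from overall stopping.

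The cost is wording and one set of simulations, with no extra patients or visits. The drawback is that either the stated patient savings or the stated false-stop rate will look less favourable.
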